5.10.2 Safety Analyses

If the Sponsor decides *to terminate the study based on the primary analysis results from Study Period A*, then safety data from Study Period B will be reported in the final CSR. The Study Period B safety population is defined in the beginning of Section 5.10.

If the Sponsor decides *to extend Study Period B or initiate an OLE, then safety data from Study Period B will be reported in the final CSR and safety data from the OLE will be summarized in the OLE CSR*. The OLE safety population is defined in the beginning of Section 5.10.

All the safety analyses described in Section 5.6 will be reported.

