4.10.4 Safety Analysis

The safety analysis population in Study Period A will consist of all carrier participants with at least one dose of study medication. The participants in this population will be grouped according to treatment received.

If the Sponsor decides to initiate an OLE study, safety data from Study Period B will also be used to contribute to the safety analysis in the OLE study. In this case, the safety analysis population in Study Period B will be grouped according to the treatment received in Study Period B. Safety assessments will be on the basis of adverse event reports, the results of vital signs, physical examinations, MRI evaluations, immunogenicity as measured by ADAs, and clinical laboratory tests.

Observed toxicities and adverse events will be coded and tabulated using the MedDRA; the frequencies of participants who receive active medication and those who receive placebo will be compared using descriptive statistics and reviewed for potential clinical significance and importance. Treatment-emergent adverse event tabulations will be provided overall, by severity, for serious adverse events, and further subcategorized by relationship to study drug.

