4.10.10 Analyses for Study Period B

All efficacy analyses will include data from Study Period A and Study Period B. The analysis population will be based on mITT population. The delayed-start efficacy analyses and rank-preserving structural failure time analyses will be triggered 2 years after the last efficacy visit in Study Period A.

All the safety analyses described in Section 4.10.4 will be reported.

Summaries of conduct of study and summaries of treatment group comparability/demographics and baseline characteristics will also be presented. The population is based on the Study Period B ITT population. The analyses are similar to what are specified for Study Period A and are specified in the SAP.

Pharmacokinetic and PD analyses will be handled in a similar fashion to Study Period A.

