5.6 SAFETY ANALYSES

All safety analyses of Study Period A will be performed in the safety-evaluable population (see Section 4 for definition).

As the study participants are considered treatment-exposed during the 16-week (approximately 5 half-lives) follow-up period, adverse events reported within 16 weeks after the last dose of study drug administered in Study Period A will be included in the safety analyses from Study Period A (contrary to the description in the protocol stating they will be summarized separately). At the end of Study Period B, safety analyses on

Study Period A will be refreshed (*due to the additional 16-week safety follow-up data accrued in Period A after the primary analysis*) and reported in the final CSR.

Adverse events reported within 16 weeks after the last dose of study drug administered in Study Period B will be included in the safety analyses on Study Period B.

Safety analyses of Study Period B and/or of the potential OLE data are summarized in Section 5.10.2.

Safety will be assessed through summaries of exposure to study treatment, adverse events, changes in laboratory test results, MRI findings, changes in vital signs and ECGs, and changes in suicidality assessment.

Study treatment exposure (such as treatment duration, total dose received, and dose modifications) will be summarized with descriptive statistics.

All verbatim adverse event terms will be mapped to MedDRA thesaurus terms, and adverse event severity will be graded according to National Cancer Institute Common Terminology Criteria for Adverse Events (NCI CTCAE), v4.0. All adverse events, serious adverse events, adverse events leading to death, adverse events of special interest, and adverse events leading to study treatment discontinuation that occur on or after the first dose of study treatment (i.e., treatment-emergent adverse events) will be summarized. All adverse events will be summarized by severity and by relationship to study drug. For events of varying severity, the highest grade will be used in the summaries.

Relevant laboratory, vital signs (pulse rate, respiratory rate, blood pressure, pulse oximetry, and temperature), and ECG data will be displayed by time, with grades identified where appropriate. Additionally, a shift table of selected laboratory tests will be used to summarize the baseline and maximum post-baseline severity grade.

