5.6.2 Adverse Events

All treatment-emergent adverse events, serious adverse events, adverse events leading to death, protocol-specified adverse events of special interest (including amyloid-related imaging abnormalities—edema/effusion [ARIA-E], amyloid-related imaging abnormalities— hemosiderin deposition [ARIA-H], cerebral macrohemorrhages, pneumonia, *potential drug-induced liver injury, and suspected transmission of infectious agents by the investigational product*) and adverse events leading to study treatment discontinuation will be summarized by MedDRA Preferred Term, appropriate thesaurus level by treatment arm. Adverse events will be summarized by severity and by relationship to study drug. For events of varying severity, the highest grade will be used in the summaries.

In addition, treatment-emergent injection reactions, infusion-related reactions and COVID-19 infections will be summarized by treatment group.

Only treatment-emergent adverse events will be included in the analyses, defined as any adverse event reported during or after the first dose of study drug. Adverse events with a missing onset date will be considered to be treatment-emergent. Adverse events with a partially missing onset date will also be included as treatment-emergent if the month (if it was recorded) and the year occur on or later than the month and year of the study treatment start date.

A separate listing of adverse events reported during the screening period (before the first dose of study drug) will also be produced.

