5.10 ANALYSES FOR PERIOD B AND OPEN-LABEL EXTENSION STUDY

This section will pre-specify the main analyses planned for Study Period B of this study and the potential OLE study.

If the Sponsor decides to terminate the study based on the primary analysis results from Study Period A, all the data and analyses from Study Period B will be considered as exploratory in nature; a final CSR will be written, including these extra data. However, if the Sponsor decides to extend Study Period B or initiate an OLE study, a planned data snapshot will occur 2 years after finished the last efficacy visit in Study Period A.

Three analysis populations are defined for this snapshot:

- Study Period A mITT population: the mITT population defined in Section 4: all randomized participants who received at least 1 dose of study drug; participants are grouped according to the treatment assignment at randomization; all efficacy analyses in this snapshot are based on mITT population among the mutation carriers
- Study Period B safety population: all randomized participants that received at least 1 dose of study drug in Study Period B; participants are grouped according to the actual treatment received; participants on placebo who received more than 2 doses of crenezumab will be grouped in the crenezumab arm
- OLE safety population: all OLE enrolled participants that received at least 1 dose of study drug (crenezumab)

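### If Period B runs past the Period A results, its adverse-event tables compare crude participant frequencies although the disclosure rule shortens counted follow-up only in the placebo (non-carrier) group

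*SAP*

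**What the plan says.** SAP 5.10.2 covers Period B safety by reference: "All the safety analyses described in Section 5.6 will be reported". On continuation, the same section provides for a choice "to extend Study Period B or initiate an OLE, then safety data from Study Period B will be reported in the final CSR". Protocol 4.10.10 does the same: "All the safety analyses described in Section 4.10.4 will be reported".

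The inherited summaries are counts of participants. Protocol 4.10.4 says "the frequencies of participants who receive active medication and those who receive placebo will be compared using descriptive statistics", and SAP 5.6.2 says events "will be summarized by MedDRA Preferred Term, appropriate thesaurus level by treatment arm". Neither document plans a rate per person-time or a time-to-event summary for adverse events.

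On grouping, SAP 5.10 defines the Period B safety population: "participants are grouped according to the actual treatment received; participants on placebo who received more than 2 doses of crenezumab" move to the crenezumab group. All carriers receive crenezumab in Period B and all non-carriers receive placebo (Protocol 3.1), so the comparison is carriers against non-carriers.

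On counted time, SAP 5.6 states: "Adverse events reported within 16 weeks after the last dose of study drug administered in Study Period B will be included". That sentence refers to the Period B safety analyses.

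On disclosure, Protocol 3.9 offers genetic results once all Week 260 assessments are done and Period A results are available. A non-carrier who takes up the offer receives no further placebo (Protocol 3.9 and 6.10). No rule stops dosing in a carrier who does so.

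On length, SAP 1.2.2 foresees about 12 months but allows extension, and Protocol 3.1 allows up to about 3–3.5 years. SAP 5.10 adds: "if the Sponsor decides to extend Study Period B or initiate an OLE study, a planned data snapshot will occur 2 years after". The interval runs from the final Period A efficacy visit.

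**The concern.** A crude proportion with an event depends on how long people are watched. In an extended Period B, one written rule ends dosing early in one group only, and the analysis window then closes 16 weeks later. Two groups with the same event rate can therefore show different frequencies.

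Long-term safety is a stated Period B objective (Protocol 2.5), and these tables are where a reader of the final report would look for it. At stake is the reading of a descriptive safety table. The Period A safety comparison and all efficacy conclusions are untouched. If Period B ends when results are known, the rule has essentially no effect.

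**Working it through.** The plan states no adverse-event rate or incidence, so there is no figure to reproduce. The calculation below shows how large the artefact could be when the true rates are identical.

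**Inputs from the documents**
- Period B length: 3.25 years, the midpoint of 3–3.5 (Protocol 3.1).
- Window after last dose: 16/52 = 0.308 years (SAP 5.6).
- Snapshot: taken as 2.0 years of follow-up (SAP 5.10).
- Group sizes: 252 recruited (Protocol 3.2) and 84 per carrier arm (the simulation setting in SAP Appendix 2), giving 168 carriers and 252 − 168 = 84 non-carriers. That all of them enter Period B is an assumption.

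**Inputs assumed**
- Event rate 0.10 per year in both groups.
- Informed non-carriers stop at 0.75–1.25 years (SAP 1.2.2 implies results within about 12 months).
- Disclosure uptake of 10% and 25%, with 50% as an upper case, because most of the kindred do not wish to know their genotype (Protocol 4.2).

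**Formula.** Proportion with an event by time t: p(t) = 1 − exp(−rate × t). The placebo proportion at uptake f is (1 − f) × p(full time) + f × p(stop time + 0.308).

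**Final report, all carriers staying.** Crenezumab: p(3.25 + 0.308) = 1 − exp(−0.3558) = 29.9%. Informed non-carriers: p(1.058) = 10.0% to p(1.558) = 14.4%.

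| Uptake | Placebo, final report | Risk ratio | Gap in placebo participants (of 84) | Risk ratio, 2-year snapshot |
|---|---|---|---|---|
| 10% | 27.9–28.4% | 1.05–1.07 | 1.3–1.7 | 1.02–1.05 |
| 25% | 25.0–26.1% | 1.15–1.20 | 3.3–4.2 | 1.05–1.13 |
| 50% | 20.0–22.2% | 1.35–1.50 | 6.5–8.4 | 1.11–1.29 |

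The snapshot column compares 1 − exp(−0.20) = 18.1% on crenezumab with 17.3–17.8%, 16.1–17.2% and 14.1–16.3% on placebo. Varying the rate over 0.05–0.20 per year gives final-report ratios of 1.05–1.07, 1.14–1.21 and 1.31–1.52.

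**Against sampling noise.** The standard error of the difference is √[p₁(1 − p₁)/168 + p₂(1 − p₂)/84]. With stopping at 1 year it is 6.0, 5.9 and 5.7 percentage points at the three uptakes. For a rare event at an assumed 0.005 per year, the gap is about 0.5 placebo participants or fewer even at 50% uptake.

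**Direction.** If 25% stop early in both groups, the ratio is 1.00. If 50% of carriers and 25% of non-carriers stop early, it is 20.0/25.0 = 0.80 to 22.2/26.1 = 0.85.

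**Does person-time cure it?** Take identical hazards, 3.25 years and stopping at 0.75 years.
- Constant hazard of 0.10: both groups give 10.0 per 100 participant-years.
- Front-loaded hazard (Weibull, shape 0.5, scale 10 years): crude ratios are 1.11 at 25% uptake and 1.24 at 50%. Person-time rates are 18.6 against 20.1 (ratio 0.93) and 18.6 against 22.2 (ratio 0.84). The true proportion at 3.25 years is 1 − exp(−√0.325) = 43.5%, and simulated Kaplan-Meier means were 43.4–43.6% in both groups at both uptakes.

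Person-time alone can therefore replace one bias with another of opposite sign. Kaplan-Meier does not, provided stopping is unrelated to event risk.

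**The case against.** The best case for the plan has five parts.

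- **No comparative aim.** The Period A safety objective compares crenezumab with placebo (Protocol 2.2), but the Period B objective names no comparator (Protocol 2.5). Non-carriers stay on placebo so that nobody is forced to learn their genotype (Protocol 3.9). Crenezumab frequencies on their own are not distorted by non-carriers stopping. This lowers the stakes, but Protocol 4.10.10 still imports the active-versus-placebo comparison of 4.10.4.
- **Stated scope.** SAP Section 1 promises only general descriptions of Period B safety analyses, and Period B analyses become exploratory if the study is terminated on the Period A results (SAP 5.10). This is fair, but the extended case is planned for, and Protocol Version 11 was amended to allow it.
- **Unequal follow-up would be visible.** A reader might infer that the counts stand alone. They do not: SAP 5.6.1 summarizes treatment duration, and SAP 5.10.3 repeats for Period B the discontinuation summaries and reasons of 5.7.1. This stands. Two gaps remain: the 5.6.1 end-dates are worded for Period A, and neither table enters an event summary.
- **Probably small.** Uptake is not given, and Protocol 4.2 points to the low end. At 10% the gap is under 2 participants and well inside one standard error. This also stands.
- **Person-time is not the cure.** The front-loaded check bears this out, so a rate column should not be the main remedy.

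A reader might also infer that the tables will overstate harm on crenezumab. The disclosure rule alone pushes that way. But carriers may also learn their status (Protocol 3.8), leave for an extension that only carriers are expected to enter (SAP 5.10.1.2), or stop after progressing. The documents do not settle the net direction.

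**Conclusion.** The point holds as a low-cost improvement, worth considering, and only for a Period B that continues past the Period A results. In that case the crude adverse-event comparison can differ between groups with no difference in true rates, and no planned event summary accounts for it.

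The size rests on assumed uptake, carrier retention and event rate. With all carriers staying, risk ratios are 1.05–1.07 at 10% uptake and 1.15–1.20 at 25%; 50% uptake (1.35–1.50) is an upper case. With heavier carrier stopping the ratio falls below 1. At 10–25% uptake the artefact is smaller than one standard error, but it is systematic and foreseeable.

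The documents do not support reading this as a known bias against crenezumab, as a flaw in Period A safety, or as something that time-at-risk adjustment makes causal. The contrast stays non-randomized and confounded with genotype whatever summary is used.

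**What to change.** In SAP 5.10.2, for a Period B that continues past the Period A results:

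1. Add Kaplan-Meier time-to-first-event summaries for any adverse event, any serious adverse event and clinically detected events of special interest. Count from first Period B dose to the earliest of first event, last dose plus 16 weeks, or data cutoff.
2. Beside the crude counts, give first events per 100 participant-years at risk with 95% CIs, as a secondary column.
3. Define Period B treatment duration explicitly, since SAP 5.6.1 ends at Period A completion.
4. Report MRI-detected ARIA per participant scanned, because Period B schedules one scan, at Week 105 or at early termination if sooner (Protocol Appendices 5 and 6).
5. Label the contrast as non-randomized, carriers against non-carriers.

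The cost is SAP wording, one more column per Period B table and a few more tables, all from dates already collected. The limits should be stated with the results: Kaplan-Meier assumes that stopping is unrelated to event risk, and the rates assume a roughly constant hazard.

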5.10.3 Other Analyses

Summaries of conduct of study and summaries of treatment group comparability/demographics and baseline characteristics will also be presented. The population is based on either the Study Period B ITT population or the OLE ITT population, depending on whether the Sponsor initiates the OLE. The analyses are similar to what are specified for Study Period A.

Pharmacokinetic and PD analyses will be handled in a similar fashion to Study Period A.

6. SUPPORTING DOCUMENTATION

This section is not applicable, since there is no additional supporting document.

Appendix 1 Changes to Protocol-Planned Analyses

The following changes have been made in this Statistical Analysis Plan (SAP) from the latest Protocol Version 10:

- The definition of the safety population for Study Period B has been updated in the SAP
- Adverse events reported during the 16-week follow-up period in Study Period A will not be summarized separately

Appendix 2 Blinded Power Analysis and its Impact on Type I Error

This section outlines the methodology that the Sponsor used for the blinded power (BP) analysis. We then provide the evidence of family-wise type I error control when a BP analysis is performed. *More details of this methodology can be found in (Hu et al. 2022).*

METHODOLOGY

Assuming a BP analysis is performed on p continuous endpoints: $X^{(1)}, X^{(2)}, \dots, \text{and } X^{(p)}$, right before study unblinding. The goal of the BP analysis is to help ensure that the primary analysis meets the statistical power criteria defined in the protocol.

For simplicity and without loss of generality, we also assume the following:

- All endpoints are expected to decrease overtime in the mutation carrier placebo arm
- $n/2$ participants randomized to the placebo arm and $n/2$ participants randomized to the mutation carrier experimental arm, with no dropout
- Change from baseline scores at the last visit are calculated from each participant (statistic denoted as $X_i^{(k)}$ for the k^{th} endpoint for the i^{th} participant), with $X_i^{(k)} \sim N(\mu_{pbo}^{(k)}, \sigma^{(k)2})$ if participant i is from the placebo arm and $X_i^{(k)} \sim N(\mu_{exp}^{(k)}, \sigma^{(k)2})$ if participant i is from the experimental arm
- **The same treatment effect in relative reduction (RR) scale R_a is assumed in the analysis across endpoints** (note that R_a differs from the true underlying treatment effect $R^{(k)} = \frac{\mu_{pbo}^{(k)} - \mu_{exp}^{(k)}}{\mu_{pbo}^{(k)}} * 100\%$)

From Friede and Kieser (2013), the scaled sample variance $\frac{n-1}{\sigma^{(k)2}} S^{(k)2} \sim \text{Noncentral chi-squared distribution with } n-1 \text{ degrees of freedom and noncentrality parameter}$

$n(\frac{\mu_{pbo}^{(k)} R^{(k)}}{4\sigma^{(k)2}})^2$ and

$$E(S^{(k)2}) = \sigma^{(k)2} + \frac{n}{4(n-1)} \left(\frac{\mu_{pbo}^{(k)} R^{(k)}}{4\sigma^{(k)2}} \right)^2.$$

Since the number of participants from the placebo and experimental arms both consist of $\frac{1}{2}$ of the total population, respectively, then we can construct the following equation.

$$\frac{\hat{\mu}_{pbo}^{(k)} + \hat{\mu}_{pbo}^{(k)}(1-R_a)}{2} = \bar{X}^{(k)}.$$

From the previous 2 equations, we can estimate the placebo mean decline and standard deviation for endpoint k :

$$\hat{\mu}_{pbo}^{(k)} = \frac{2\bar{X}^{(k)}}{2-R_a}$$

$$\hat{\sigma}^{(k)2} = S^{(k)2} - \frac{n}{4(n-1)} \left(\frac{2R_a \bar{X}^{(k)}}{2-R_a} \right)^2.$$

When we assume the same relative treatment effect R_a across p continuous endpoints, finding the endpoint with the highest statistical power is equivalent to finding the endpoint with the smallest CV in the placebo arm. We have:

$$\begin{aligned} \widehat{CV}^{(k)} &= \frac{\sqrt{\hat{\sigma}^{(k)2}}}{\hat{\mu}_{pbo}^{(k)}} = \sqrt{\left(\frac{2-R_a}{2}\right)^2 \frac{S^{(k)2}}{\bar{X}^{(k)2}} - \frac{nR_a^2}{4(n-1)}} \\ &= \sqrt{\left(\frac{2-R_a}{2}\right)^2 \widehat{CV}_{pooled}^{(k)2} - \frac{nR_a^2}{4(n-1)}}. \end{aligned}$$

We can see that $\widehat{CV}^{(k)}$ is a monotonically increasing function of $\widehat{CV}_{pooled}^{(k)2}$, which implies that endpoints can be evaluated based on their relative $\widehat{CV}_{pooled}^{(k)2} = \frac{S^{(k)2}}{\bar{X}^{(k)2}}$ using the blinded data.

The BP analysis just described in the proceeding bears similarities to blinded sample size re-estimation. In blinded sample size re-estimation, the updated sample size depends on the targeted treatment effect and observed pooled sample variance. Likewise, our BP analysis depends on multiple targeted treatment effects and the observed pooled CVs. It is important to note that neither case requires unblinded data.

It has been reported that blinded sample size re-estimation does not lead to substantive type I error inflation (Friede and Kieser 2006; Glimm and Läuter 2013). Next, we prove that analytically, BP analysis controls family-wise error rate (FWER) in *both the strong* the weak sense. We then provide simulations which support FWER control in the strong sense.

TYPE I ERROR CONTROL UNDER BP ANALYSIS

We present the theorem under the assumption that *at least one of the p endpoints has no treatment effect*.

Theorem 1

Among the p endpoints $\{X^{(1)}, X^{(2)}, \dots, X^{(p)}\}$ in the BP analysis, if there is at least one endpoint that has no treatment effect, the family-wise type I error is controlled under the BP analysis.

Proof: We start by writing out the density function of the endpoint vector for participant i . If we define the endpoint vector $X_i = [X_i^{(1)}, X_i^{(2)}, \dots, X_i^{(p)}]^T$ and if we assume

the endpoints considered follow a multi-normal distribution, then we have that $X_i \sim N(L_i \mu, \Sigma)$, where:

$$L_i = \begin{bmatrix} l_i & 0 & \dots & 0 & 1-l_i & 0 & \dots & 0 \\ 0 & l_i & \dots & 0 & 0 & 1-l_i & \dots & 0 \\ \vdots & \vdots & \ddots & \vdots & \vdots & \vdots & \ddots & \vdots \\ 0 & 0 & \dots & l_i & 0 & 0 & \dots & 1-l_i \end{bmatrix},$$

$$\mu = \left[\mu_{pbo}^{(1)}, \mu_{pbo}^{(2)}, \dots, \mu_{pbo}^{(p)}, \mu_{exp}^{(1)}, \mu_{exp}^{(2)}, \dots, \mu_{exp}^{(p)} \right]^T,$$

$$\Sigma = \begin{bmatrix} \sigma^{(1)}^2 & \dots & \sigma^{(1)(p)} \\ \vdots & \ddots & \vdots \\ \sigma^{(1)(p)} & \dots & \sigma^{(p)}^2 \end{bmatrix}.$$

The constant l_i takes the value of either 0 or 1 (participant i in the experimental group or placebo group). We denote the parameter vector $\theta = (\mu^T, \text{vec}(\Sigma)^T)^T$. We also denote $\mu_{pbo} = \left[\mu_{pbo}^{(1)}, \mu_{pbo}^{(2)}, \dots, \mu_{pbo}^{(p)} \right]^T$ and $\mu_{exp} = \left[\mu_{exp}^{(1)}, \mu_{exp}^{(2)}, \dots, \mu_{exp}^{(p)} \right]^T$. The density function of X_i is:

$$f(X_i | \theta, L_i) = \frac{1}{\sqrt{(2\pi)^p |\Sigma|}} \exp \left(-\frac{1}{2} (X_i - L_i \mu)^T \Sigma^{-1} (X_i - L_i \mu) \right).$$

We define functions:

$$\eta(\theta) = \begin{pmatrix} \Sigma^{-1} \mu_{pbo} \\ \Sigma^{-1} \mu_{exp} \\ -\frac{1}{2} \Sigma^{-1} \end{pmatrix},$$

$$T(X_i) = \begin{pmatrix} L_i^T X_i \\ X_i X_i^T \end{pmatrix},$$

$$h(X_i) = (2\pi)^{-\frac{p}{2}},$$

$$A(\theta) = \frac{1}{2} (L_i \mu)^T \Sigma^{-1} L_i \mu + \frac{1}{2} \log |\Sigma|.$$

The dot product between $\eta(\theta)$ and $T(X_i)$ is calculated as:

$$\eta(\theta) \cdot T(X_i) = \begin{pmatrix} \Sigma^{-1} \mu_{pbo} \\ \Sigma^{-1} \mu_{exp} \end{pmatrix}^T L_i^T X_i + \left\langle \left(-\frac{1}{2} \Sigma^{-1} \right)^T, X_i X_i^T \right\rangle_F = \mu^T L_i^T \Sigma^{-1} X_i - \frac{1}{2} \text{tr}(\Sigma^{-1} X_i X_i^T),$$

where $\langle \cdot, \cdot \rangle_F$ is the Frobenius inner product and “ $\text{tr}(\cdot)$ ” stands for the trace of a matrix. The density function can then be written as:

$$\begin{aligned} f(X_i|\theta, L_i) &= (2\pi)^{-\frac{p}{2}} \exp\left(-\frac{1}{2}(X_i - L_i\mu)^T \Sigma^{-1}(X_i - L_i\mu) - \frac{1}{2}\log|\Sigma|\right) \\ &= h(X_i) \exp(\eta(\theta) \cdot T(X_i) - A(\theta)). \end{aligned}$$

Therefore, the multivariate normal distribution is in the exponential family with the parameter defined as $\theta = (\mu^T, \text{vec}(\Sigma)^T)^T$. The statistic $\sum_{i=1}^n T(X_i) = \begin{pmatrix} \sum_{i=1}^n L_i^T X_i \\ \sum_{i=1}^n X_i X_i^T \end{pmatrix}$ is then both complete and sufficient for θ (Theorems 6.2.10 and 6.2.25 from Casella and Berger 2021). The final t-test statistic t_k is clearly free of the parameter vector θ ; therefore, t_k is an ancillary statistic to θ . Based on Basu's theorem, the testing statistic t_k is independent of $\sum_{i=1}^n T(X_i)$. Since the statistics $\frac{S^{(k)2}}{(\bar{X}^{(k)})^2}$ ($k = 1, 2, \dots, p$) in the BP analysis are all functions of $\sum_{i=1}^n T(X_i)$, then the testing statistic t_k is also independent of $\frac{S^{(k)2}}{(\bar{X}^{(k)})^2}$ ($k = 1, 2, \dots, p$).

We assume the final t-test is a two-sided test with the significance level of 0.05. If the experimental drug has no effect on all p endpoints, then the family-wise type I error is:

$$\begin{aligned} \alpha &= \sum_{k=1}^p P\left(\frac{S^{(k)2}}{(\bar{X}^{(k)})^2} = \min\left\{\frac{S^{(1)2}}{(\bar{X}^{(1)})^2}, \frac{S^{(2)2}}{(\bar{X}^{(2)})^2}, \dots, \frac{S^{(p)2}}{(\bar{X}^{(p)})^2}\right\}, |t_k| \geq t_{0.05,n-2}\right) \\ &= \sum_{k=1}^p P\left(\frac{S^{(k)2}}{(\bar{X}^{(k)})^2} = \min\left\{\frac{S^{(1)2}}{(\bar{X}^{(1)})^2}, \frac{S^{(2)2}}{(\bar{X}^{(2)})^2}, \dots, \frac{S^{(p)2}}{(\bar{X}^{(p)})^2}\right\}\right) \\ &\quad * P(|t_k| \geq t_{0.05,n-2}) = 1 * 0.05 = 0.05. \end{aligned}$$

If the experimental drug has no effect only in the first l endpoint (without loss of generality) but has effect in the remaining endpoints, then the family-wise type I error is:

$$\begin{aligned} \alpha &= \sum_{k=1}^l P\left(\frac{S^{(k)2}}{(\bar{X}^{(k)})^2} = \min\left\{\frac{S^{(1)2}}{(\bar{X}^{(1)})^2}, \frac{S^{(2)2}}{(\bar{X}^{(2)})^2}, \dots, \frac{S^{(p)2}}{(\bar{X}^{(p)})^2}\right\}, |t_k| \geq t_{0.05,n-2}\right) \\ &= \sum_{k=1}^l P\left(\frac{S^{(k)2}}{(\bar{X}^{(k)})^2} = \min\left\{\frac{S^{(1)2}}{(\bar{X}^{(1)})^2}, \frac{S^{(2)2}}{(\bar{X}^{(2)})^2}, \dots, \frac{S^{(p)2}}{(\bar{X}^{(p)})^2}\right\}\right) \\ &\quad * P(|t_k| \geq t_{0.05,n-2}) \leq 1 * 0.05 = 0.05. \end{aligned}$$

We have proved that the family-wise type I error is not inflated under the BP analysis, both in the strong and weak sense.

Next, we show through simulations *to support the proof*. For simplicity, we assume the BP analysis is performed on 2 endpoints X and Y , where the experimental drug has no treatment effect on X but *could have* a treatment effect on Y .

Mimicking study GN28352, we assume the following:

- 84 participants randomized to the placebo arm and 84 participants randomized to the experimental arm, with no dropout
- Endpoints X and Y both follow a normal distribution within each arm
- Within endpoints X and Y , without loss of generality, the standard deviation in both arms is 1
- Endpoint X has no treatment effect and the placebo arm mean is 1/0.65 (protocol CV assumption on API ADAD Composite Cognitive Test total score=0.65)

In the simulation study, we vary the following, which yields 135 scenarios:

- Treatment effect in endpoint Y in RR scale: 0%, 50%, and 100%
- Placebo mean in endpoint Y : 0, 1, 1.5, 2, 10
- *Endpoints X and Y follow a bivariate normal distribution with*
 - Correlation between endpoint X and Y within the placebo group: $\rho_{pbo}=0.1, 0.5, 0.9$
 - Correlation between endpoint X and Y within the treatment group: $\rho_{exp}=0.1, 0.5, 0.9$

The family-wise type I error in this case equals the probability of rejecting the null H_0 in endpoint X . *When there is a treatment effect in endpoint Y , the only scenario where a type I error can happen is when endpoint X is chosen by the BP analysis.* The number of iterations in the simulation study was 100,000. We summarize the simulation results on type I error (along with the probability of choosing endpoint Y *in scenarios where endpoint Y has a treatment effect*) in [Tables 1–3](#).

Table 1 Family-Wise Strong Type I Error, Assuming 0% Treatment Effect in Endpoint Y (Type I Error in the Weak Sense)

		Placebo Mean in Endpoint Y				
		0	1	1.5	2	10
$\rho_{pbo} = 0.1$	$\rho_{exp} = 0.1$	0.05090	0.04968	0.0583	0.04965	0.04862
	$\rho_{exp} = 0.5$	0.04928	0.04963	0.04995	0.05029	0.04983
	$\rho_{exp} = 0.9$	0.05042	0.04981	0.05012	0.04894	0.05068
$\rho_{pbo} = 0.5$	$\rho_{exp} = 0.1$	0.04949	0.04898	0.04953	0.04982	0.05075

		Placebo Mean in Endpoint Y				
	$\rho_{exp} = 0.5$	0.05052	0.05048	0.05014	0.04953	0.04962
	$\rho_{exp} = 0.9$	0.04913	0.05105	0.05016	0.04927	0.04969
$\rho_{pbo} = 0.9$	$\rho_{exp} = 0.1$	0.05074	0.05068	0.05055	0.04959	0.05099
	$\rho_{exp} = 0.5$	0.05010	0.05002	0.05012	0.04951	0.05088
	$\rho_{exp} = 0.9$	0.04969	0.05063	0.04900	0.05004	0.04970

Table 2 Family-Wise Strong Type I Error with Probability of Choosing Endpoint Y under the Blinded Power Analysis, Assuming 50% Treatment Effect in Endpoint Y (Type I Error in the Strong Sense)

		Placebo Mean in Endpoint Y				
		0	1	1.5	2	10
$\rho_{pbo} = 0.1$	$\rho_{exp} = 0.1$	0.04927 (0%)	0.05127 (0%)	0.05072 (0.03%)	0.04689 (9.0%)	0.00000 (100%)
	$\rho_{exp} = 0.5$	0.04948 (0%)	0.05005 (0%)	0.04937 (0%)	0.04570 (6.5%)	0.00000 (100%)
	$\rho_{exp} = 0.9$	0.04993 (0%)	0.05038 (0%)	0.05005 (0%)	0.04308 (2.9%)	0.00000 (100%)
$\rho_{pbo} = 0.5$	$\rho_{exp} = 0.1$	0.04936 (0%)	0.04950 (0%)	0.05061 (0.01%)	0.04590 (8.1%)	0.00000 (100%)
	$\rho_{exp} = 0.5$	0.04934 (0%)	0.04995 (0%)	0.04996 (0%)	0.04585 (5.4%)	0.00000 (100%)
	$\rho_{exp} = 0.9$	0.05039 (0%)	0.05019 (0%)	0.04961 (0%)	0.04601 (1.9%)	0.00000 (100%)
$\rho_{pbo} = 0.9$	$\rho_{exp} = 0.1$	0.04943 (0%)	0.05038 (0%)	0.05132 (0%)	0.04672 (5.8%)	0.00000 (100%)
	$\rho_{exp} = 0.5$	0.04975 (0%)	0.05020 (0%)	0.04959 (0%)	0.04746 (3.0%)	0.00000 (100%)
	$\rho_{exp} = 0.9$	0.05086 (0%)	0.04916 (0%)	0.04940 (0%)	0.04895 (0.4%)	0.00000 (100%)

Table 3 Family-Wise Strong Type I Error with Probability of Choosing Endpoint Y under the Blinded Power Analysis, Assuming 100% Treatment Effect in Endpoint Y (Type I Error in the Strong Sense)

		Placebo Mean in Endpoint Y				
		0	1	1.5	2	10
$\rho_{pbo} = 0.1$	$\rho_{exp} = 0.1$	0.05030 (0%)	0.05097 (0%)	0.05008 (0%)	0.05070 (0%)	0.04979 (0%)
	$\rho_{exp} = 0.5$	0.04990 (0%)	0.04985 (0%)	0.04988 (0%)	0.05013 (0%)	0.04838 (0%)
	$\rho_{exp} = 0.9$	0.04908 (0%)	0.04976 (0%)	0.05006 (0%)	0.05013 (0%)	0.05044 (0%)
$\rho_{pbo} = 0.5$	$\rho_{exp} = 0.1$	0.04964 (0%)	0.05094 (0%)	0.05063 (0%)	0.05004 (0%)	0.04949 (0%)
	$\rho_{exp} = 0.5$	0.05021 (0%)	0.05089 (0%)	0.05002 (0%)	0.05042 (0%)	0.05016 (0%)
	$\rho_{exp} = 0.9$	0.04965 (0%)	0.04976 (0%)	0.05033 (0%)	0.04960 (0%)	0.05064 (0%)
$\rho_{pbo} = 0.9$	$\rho_{exp} = 0.1$	0.05039 (0%)	0.05153 (0%)	0.04978 (0%)	0.05014 (0%)	0.04924 (0%)
	$\rho_{exp} = 0.5$	0.05148 (0%)	0.04994 (0%)	0.04925 (0%)	0.04939 (0%)	0.05031 (0%)
	$\rho_{exp} = 0.9$	0.04936 (0%)	0.05032 (0%)	0.05038 (0%)	0.04999 (0%)	0.05082 (0%)

As seen from Tables 1–3, the simulated family-wise type I errors are at or substantially below 0.05. Also in scenarios where the treatment effect in Y is non-zero, when the probability of choosing endpoint Y approaches to 100%, the family-wise type I error approaches to 0%; this can be seen in the proof in Theorem 1.

We conclude that the BP analysis does not inflate family-wise type I error both weakly or strongly.

